1 PROTOCOL SUMMARY

1.1 Study design

The study is a non-randomized, open label, prospective multi-center, clinical study designed to collect long-term (1 year), system-related, clinical and subject reported outcome data from subjects indicated for a de novo ablation of paroxysmal atrial fibrillation and treated with the Cryterion Cardiac Cryoablation System and components including the SmartFreeze Cryo-console, the Cryoablation Balloon Catheter, and the Circular Mapping catheter.

A protocol amendment of the original FIM protocol was initiated in May 2018 designed for the purpose of obtaining CE mark and intended to prolong the follow-up period from 30 days to 12 months and extend the number of enrolled subjects from 30 to 100.

Subjects will be followed for 12 months by each clinical center with specific scheduled visits to detect recurrent AF (Detectable AF) and adverse events (AEs).

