2 SUBJECT CLASSIFICATION DEFINITIONS

For the purposes of this clinical study, the following definitions regarding the status of a subject will apply:

Enrolled Subject - Any subject who has signed an informed consent form (ICF)

Consent Ineligible Subject – Any subject who has signed the informed consent but is found not to meet all the inclusion/exclusion criteria. This includes a subject who has signed an informed consent form but may be excluded based on the results of the pre-procedure TEE or intracardiac echocardiogram (ICE) evaluation of the left atrial appendage (LAA) and/or PV anatomy. In the event these subjects completed a trans-septal puncture, they will be followed through discharge for the recording of any procedure related adverse events. These subjects will not count towards the enrollment ceiling and will not be considered for the primary endpoints analysis.

Intent Subject – Any subject who has signed an informed consent form (ICF) and is deemed study eligible by meeting all the inclusion and none of the exclusion criteria but does not undergo the ablation procedure. This subject will be withdrawn from the study. Data will be collected up to the point of withdrawal, will not count towards the enrollment ceiling and will not be considered for primary endpoints analysis.

Attempt Subject - Any subject who has signed an informed consent form (ICF) and is deemed study eligible by meeting all the inclusion and none of the exclusion/criteria and undergoes the ablation procedure with any of the investigational device entered in the subjects' body but no energy is delivered to the PVs. This subject will be followed through the 30 days follow up then withdrawn from the study. Data will be collected up to the point of withdrawal, will not count towards the enrollment ceiling and will not be considered for primary endpoints analysis.

Treated Subject – Any screened subject who completes the ablation procedure to the point that any of the investigational products are introduced into the body and Cryo-energy is delivered. Enrolled subjects will be followed for all study outcome measures for the full duration of the clinical study.

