3.4 Primary Effectiveness Endpoint

The primary effectiveness endpoint is acute success defined as rate of successful pulmonary vein electrical isolation with confirmation of entrance/exit block.

The rate of acute success will be presented as a binomial rate (N events/ N subjects) with corresponding exact binomial 95% confidence interval. The rates will be compared to the acute success rates derived from available literature data.

The primary effectiveness endpoint will be assessed in all enrolled subjects who undertake the ablation procedure to the point that the Cryoablation Balloon is used to deliver at least one cryo application (Treated subjects).

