3.5 Additional Effectiveness Endpoint

The additional effectiveness endpoint is 12 month treatment success, defined as the proportion of subjects free from symptomatic atrial arrhythmias at 12 months.

The rate of 12 month success will be presented as a binomial rate (N events/ N subjects) with corresponding exact binomial 95% confidence interval. The rates will be compared to the 12 month success rates derived from available literature data.

The additional effectiveness endpoint will be assessed in all enrolled subjects who undertake the ablation procedure to the point that the Cryoablation Balloon is used to deliver at least one cryo application (Treated subjects). Subjects who withdraw from the study prior to their 12 month visit without experiencing an event will be considered ineligible for this analysis.

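### Section 2 separates Attempt from Treated on two different energy thresholds, so an eligible subject given cryo-energy but none to a pulmonary vein falls in both classes

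*SAP*

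**What the plan says.** SAP section 2 (Subject Classification Definitions) describes an Attempt subject as someone who has consented, meets all eligibility criteria and "undergoes the ablation procedure with any of the investigational device entered in the subjects' body but no energy is delivered to the PVs". Of this class it says: "This subject will be followed through the 30 days follow up then withdrawn from the study". It adds that the class "will not count towards the enrollment ceiling and will not be considered for primary endpoints analysis".

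The same section describes a Treated subject as a screened subject in whom "any of the investigational products are introduced into the body and Cryo-energy is delivered". No site of delivery is named. The follow-up sentence under that definition reads: "Enrolled subjects will be followed for all study outcome measures for the full duration of the clinical study". Section 1.1 gives the duration: "Subjects will be followed for 12 months by each clinical center".

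Section 3.4 sets the population for acute success as enrolled subjects in whom "the Cryoablation Balloon is used to deliver at least one cryo application (Treated subjects"). Section 3.5 has a matching rule for 12-month success, again needing only a single application: "The additional effectiveness endpoint will be assessed in all enrolled subjects who undertake the ablation procedure to the point that the Cryoablation Balloon is used". Neither section requires that an application be at a pulmonary vein. Section 3.3 assesses primary safety in Attempt and Treated subjects alike, once the balloon has been inserted.

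**The concern.** Attempt is bounded by where the energy went. Treated is bounded by whether any energy was delivered. These are different conditions, and the SAP does not say which prevails when both are met. The subject caught between them is eligible, received cryo-energy, and received none at a vein, for example because the balloon was displaced for the only freeze given.

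The two labels lead to opposite handling of a subject in whom the system did not reach its target. Under section 2, the Attempt label takes the subject out of the primary endpoints and the enrollment ceiling and ends follow-up after 30 days. Under 3.4 and 3.5, the same subject is in both effectiveness denominators as a failure. If section 2 were allowed to govern, the discrepancy could only favour the device. It would also cut short observation for a safety endpoint that section 1.4.1 sets at 12 months.

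**Working it through.** The SAP states no figure for this point, so there is nothing to reproduce. The check is a comparison of definitions, followed by an illustration of size.

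**Step 1: the definitions as sets.** Let D = an investigational device in the body, E = cryo-energy delivered anywhere, P = energy delivered to a pulmonary vein.

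- Attempt (section 2) = eligible and D and not P.
- Treated (section 2) = D and E. Sections 3.4 and 3.5 keep E, specified as one or more applications from the balloon.
- Intersection = eligible and D and E and not P.

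No wording in the SAP makes this intersection empty, declares the classes mutually exclusive or ranks them.

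**Step 2: handling of a subject in the intersection.**

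| Item | As Attempt (section 2) | As Treated (section 2, 3.3 to 3.5) |
|---|---|---|
| Enrollment ceiling | Not counted | No exclusion stated |
| Acute success | Excluded with the primary endpoints | In the denominator; a failure, because 1.4.2 requires isolation of at least three veins |
| 12-month success | Withdrawn after 30 days | In the denominator; a failure, because 1.4.3 makes an acute failure a treatment failure |
| Primary safety | Included by 3.3 once the balloon is inserted | Included by 3.3 |
| Follow-up | 30 days, then withdrawal | Full duration, if the sentence on enrolled subjects is read as applying to this class |

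For 12-month success, 3.5 drops subjects who withdraw early without an event. Under 1.4.3 an acute failure is already a treatment failure, so that rule should not remove the subject. However, 3.5 does not say that acute failure counts as the event.

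**Step 3: illustration of size.** Assumptions, none of them from the SAP: exactly one subject lies in the intersection, every other subject in the set is Treated, and every other subject is an acute success. The set sizes are the 30- and 50-subject cohorts of section 3.1.1 and the 100 enrolled subjects of section 1.1. Intervals are exact binomial (Clopper-Pearson), the method named in 3.4. With x successes in n, the lower limit is the 0.025 quantile of Beta(x, n − x + 1). The upper limit is the 0.975 quantile of Beta(x + 1, n − x), or 1 when x = n.

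| n | Excluded as Attempt | Counted as Treated |
|---|---|---|
| 30 | 29/29 = 100% (88.1 to 100) | 29/30 = 96.7% (82.8 to 99.9) |
| 50 | 49/49 = 100% (92.7 to 100) | 49/50 = 98.0% (89.4 to 99.9) |
| 100 | 99/99 = 100% (96.3 to 100) | 99/100 = 99.0% (94.6 to 100.0) |

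With three such subjects in 100, the comparison is 97/97 = 100% (96.3 to 100) against 97/100 = 97.0% (91.5 to 99.4).

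**The case against.** The strongest reply is that the endpoint sections already settle the effectiveness analysis. Sections 3.4 and 3.5 each name their own population, and a subject given one off-target application meets that rule whatever section 2 calls them. This largely stands. A reader might infer that the Attempt label removes device failures from both effectiveness rates. The documents do not support that as a settled outcome, because it requires section 2 to override the endpoint-specific rules. What remains is that section 2 expressly excludes Attempt subjects from the primary endpoints and no order of precedence is given.

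A reader might also infer that these subjects are lost from primary safety. Section 3.3 says otherwise, since it takes both classes once the balloon is in. That 3.3 disagrees with the exclusion in section 2 for every Attempt subject with a balloon inserted is a wider and separate matter. Only the length of safety observation depends on the class here.

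It can be argued that section 1.4.2 ties cryo applications to the targeted veins, so that the two thresholds are one threshold loosely worded. That text defines acute success, not the analysis population, and so does not close the gap.

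The overlap is easily overstated. A console or balloon fault during a freeze does not mean that the balloon was away from a vein, and a vein that cannot be engaged does not mean that a freeze was started. Neither subject is necessarily in the intersection. Nor does the SAP support a claim that the class would be chosen once the result is known. It does not say who assigns the class or when, and whether an application was delivered is a procedural fact.

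Finally, the follow-up contrast rests partly on placement. The full-duration sentence refers to enrolled subjects, meaning anyone who signed consent. Read literally, it conflicts with the 30-day withdrawal of every Attempt subject, not only those in the overlap. This objection stands, and the point does not depend on that sentence.

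**Conclusion.** The overlap follows from the text. An eligible subject who receives cryo-energy but none at a pulmonary vein meets both definitions. Section 2 would exclude and withdraw that subject, while 3.4 and 3.5 count them as a failure on both effectiveness endpoints. Membership of the primary safety population is not affected, although withdrawal at 30 days would truncate observation for the 12-month safety endpoint.

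Severity is low. Such subjects should be rare and the SAP gives no frequency. On the illustrative assumptions, one subject moves acute success by 3.3 percentage points in 30 (100 − 96.7), 2.0 in 50 and 1.0 in 100. Section 3.2 describes the analysis as descriptive, and rates are compared with literature values, so the visible text contains no test or performance goal that would change. The sample size section is redacted and is not relied on. The point deserves correction because the definitions contradict one another, section 2's version could only favour the device, and the repair is simple.

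**What to change.** For analysis, use one energy threshold in section 2, 3.4 and 3.5. The least disruptive choice is the one already in 3.4 and 3.5: "the Cryoablation Balloon is used to deliver at least one cryo application (Treated subjects"). Among eligible subjects, Attempt would then mean that an investigational device was introduced and no cryo application was delivered. Any subject given an application would count in both effectiveness denominators. This makes the two classes exclusive among eligible subjects only, because the Treated definition carries no eligibility condition of its own.

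Separately, the sponsor should reconcile the follow-up statements in section 2: withdrawal of Attempt subjects after 30 days, and full-duration follow-up stated for enrolled subjects. Which duration should apply is for the sponsor and is not judged here.

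The cost is a wording change in the SAP and a check that the protocol definitions match. Acute and 12-month success may become slightly less favourable if any such subject exists.

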3 ENDPOINT ANALYSES

3.1 Analysis Details

3.1.1 Analysis Populations

The overall analysis of the endpoints of the study will be based on the Enrolled Subject Population. All Enrolled subjects will be included in this analysis and the analysis will be

performed when all subjects have exited the study (either reaching End of Study or having been withdrawn) and all data cleaning activities have occurred.

A sub-analysis will be performed on the first 30 enrolled subjects when they have reached 1 Month of follow up for the purpose of CE Mark. This analysis will include all data on the first 30 subjects enrolled, as determined based on their enrollment date, and will occur when all data cleaning activities on the submission data have occurred.

An additional sub-analysis will be performed on the first 50 enrolled subjects, determined by enrollment date, for the purpose of PMDA submission. The analysis will occur when the first 50 enrolled subjects have reached a minimum of 1 month of follow up and all data cleaning activities on the submission data have occurred. Submission data will include all available data on the 50 subject cohort, including up to 12 months of follow up. Enrollment date will be considered the date informed consent was signed. When determining the 50 subject cutoff, in the event more than one subject are consented on the same day if subjects are consented at the same site, the first consented subject based on subject ID number will be included. If subjects are consented at different sites both will be included.

3.1.2 Sample Size

[REDACTED]

3.1.3 Control of Bias

Selection of subjects for the overall study will be made from the Investigator's standard of care population. All subjects meeting the eligibility criteria and having signed the ICF will be eligible for enrollment in the study and all enrolled subjects will be included in the overall analysis.

Sample sizes for the sub-analyses were determined in conjunction with the corresponding regulatory body prior to performing the data analysis. Subject eligibility for each analysis was determined based on the order of subject enrollment.

3.2 Statistical Analysis

Analysis of study endpoints will be performed on an intent-to-treat basis. All partial data that is available on subjects who drop out during the course of the study will be included.

Descriptive analysis will be used to present the study. Continuous variables will be reported as median and range, mean \pm standard deviation; categorical variables will be reported as n/N (%).

3.3 Primary Safety Endpoint

The primary safety endpoint outcome is freedom from a composite MAE list, outlined in Section 2.4.1 above, and all other serious or non-serious adverse device effects (SADEs or ADEs).

The rate of MAEs and rate of SADEs and ADEs will each be presented separately as well as an overall combined rate of all events. Rates will be presented as the binomial rate (N events/ N subjects) with corresponding exact binomial 95% confidence interval. These rates will be compared to the safety outcome rates derived from available literature data.

Additionally, all adverse events will be summarized by type of event, severity, relationship to the device and/or procedure, and timing of event relative to the procedure date. Listings of all adverse events and separate listings of events meeting the safety endpoint will be provided.

The primary safety endpoint will be assessed in all enrolled subjects who undertake the ablation procedure to the point that the Cryoablation Balloon is inserted into the subject (Attempt and Treated subjects).

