1.4 Endpoints

1.4.1 Primary Safety Endpoint

Safety endpoint is assessed by freedom from device or procedure related serious adverse events (referred to as Major Adverse Events, MAE) at 12 months* post-procedure.

MAEs include the following:

- Death
- Myocardial infarction
- Cardiac perforation/ pericardial tamponade
- Cerebral infarct or systemic embolism
- Major bleeding requiring transfusion of blood products
- Mitral or tricuspid valvular damage
- Phrenic nerve damage causing persistent diaphragmatic paralysis**
- Symptomatic pulmonary vein stenosis
- Atrio-esophageal fistula
- Air embolism leading to a life-threatening event such as a ventricular arrhythmia, stroke or myocardial infarction
- Any other serious or non-serious adverse device effects (SADEs or ADEs)

*For 1 Month sub-analyses this endpoint will be presented as the rate at 1 Month. Any additional endpoint events reported for subjects with longer follow-up will be noted in the report

**According to the consensus document definition: Phrenic nerve paralysis is defined as absent phrenic nerve function as assessed by a sniff test. A phrenic nerve paralysis in this study is considered to be permanent when it is documented to be present at 12 months following ablation.

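### The label MAE covers different events in SAP sections 1.4.1 and 3.3, and the safety rates need a stated subject-level numerator and one denominator

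*SAP*

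**What the plan says.** **Definition (SAP 1.4.1).** The endpoint is "freedom from device or procedure related serious adverse events (referred to as Major Adverse Events, MAE") at 12 months. A list of MAEs follows. Its first ten bullets are specific events, from death to life-threatening air embolism. Its eleventh is "Any other serious or non-serious adverse device effects (SADEs or ADEs").

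**Analysis (SAP 3.3).** The outcome is "freedom from a composite MAE list, outlined in Section 2.4.1 above, and all other serious or non-serious adverse device effects". On reporting: "The rate of MAEs and rate of SADEs and ADEs will each be presented separately as well as an overall combined rate of all events". Each rate is a binomial rate, written as events over subjects, with an exact 95% interval. On comparison: "These rates will be compared to the safety outcome rates derived from available literature data". The analysis set is Attempt plus Treated subjects.

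**Subject classes (SAP 2).** Attempt subjects are not to be considered for analysis of the primary endpoints.

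**Sub-analyses.** For the 1-month sub-analyses, "this endpoint will be presented as the rate at 1 Month". Under 3.1.1 a "sub-analysis will be performed on the first 30 enrolled subjects" for CE Mark, and an "additional sub-analysis will be performed on the first 50 enrolled subjects" for the PMDA submission.

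**The concern.** The label MAE has two contents. In 1.4.1 every adverse device effect is an MAE, because the eleventh bullet stands in the MAE list. In 3.3 the same effects are a second component, with a rate of their own. Section 1.4.1 also disagrees with itself, since the headline admits only serious events and the eleventh bullet admits non-serious ones.

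Two further gaps affect the same rates. Adverse events can recur within a subject, so a count of events over subjects need not be a proportion. And sections 2 and 3.3 give opposite instructions on whether Attempt subjects belong to the primary safety analysis.

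At stake is what is set beside the published rates. A rate labelled MAE could be read with the wrong content, and the interval around it has the stated meaning only if numerator and denominator are counts of subjects from one agreed set. The same labels carry into the 30- and 50-subject sub-analyses.

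**Working it through.** The SAP states no event count or safety rate, so there is no figure to reproduce. The check is a comparison of the texts, with simple algebra.

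**1. The MAE label.** Let *n* be the number of subjects in the safety set, *a* the subjects with at least one of the ten named events, and *c* the subjects with another adverse device effect but no named event.

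| Rate | Content under 1.4.1 | Content under 3.3 |
|---|---|---|
| MAE | (a + c)/n | a/n |
| Combined | (a + c)/n | (a + c)/n |

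The combined rate agrees. The MAE rates differ by (a + c)/n − a/n = c/n. Under 1.4.1 the MAE row only repeats the combined row, and the device-effect row is a subset of it. The three-way split in 3.3 is informative only if MAE means the ten named events.

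**2. Serious or not.** Take a subject whose only event is a non-serious device effect.
- Headline of 1.4.1: not an endpoint event.
- Eleventh bullet of 1.4.1: an endpoint event.
- First sentence of 3.3: an endpoint event.

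Two explicit statements admit the event and one general phrase does not.

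**3. Scale of the label difference.** The SAP does not give *c*. If it is 0, the two MAE rates coincide. Each subject counted in *c* moves the MAE rate by 1/n: 1.0 percentage point if n = 100, 2.0 if n = 50 and 3.3 if n = 30. These values of *n* are assumptions, taken from the enrolment figures in 1.1 and 3.1.1. Enrolled means consented under section 2, so the safety set of 3.3 can differ from them. The arithmetic gives a scale and says nothing of how large the gap will be.

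**4. Events or subjects.** Suppose *s* subjects have *e* qualifying events between them, so e ≥ s. The exact binomial interval applies to s/n, where each subject contributes one yes or no. It applies to e/n only when e = s, that is, when no subject has more than one event. In principle *e* can exceed *n*, and e/n is then not a proportion at all.

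**5. Denominator.** With *t* Treated and *p* Attempt subjects, 3.3 gives n = t + p. Section 2 gives n = t, and it also removes from the numerator any event in an Attempt subject. The two agree only if p = 0.

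**The case against.** The best case for the plan is that 3.3 is the operative analysis text and can be followed. The split makes sense on only one reading, and a programmer would adopt it. All three rates appear together, so a reader who took MAE in the 1.4.1 sense would see the MAE and combined rows differ and notice the labelling. Section 3.3 also requires adverse event summaries and endpoint listings, from which any version can be rebuilt. The analysis is descriptive under 3.2. All of this stands, and it keeps the point minor. It does not make the two sections agree: 3.3 points to the list in 1.4.1 for its MAEs, and that list contains the very effects that 3.3 reports separately.

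On counting, the binomial wording, the n/N (%) convention in 3.2 and the same shorthand for subject-level outcomes in 3.4 and 3.5 all suggest one count per subject. That is the probable intent. A reader might infer that the plan means to put a binomial interval on event counts; the documents do not show that. But the literal wording allows it, and unlike acute success, adverse events can recur.

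Other stronger readings also fail. A reader might infer that the primary composite changes between sections; it does not, because the first sentence of 3.3 adds the other device effects back. A reader might infer that the SAP leaves the rate for comparison with literature open; the comparison sentence covers all three rates, so a demand for a single one would be a preference. The pointer to section 2.4.1 is a clerical slip for 1.4.1, with the same offset in 3.6, and the target is plain.

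**Conclusion.** Wrong as written, and minor. The primary safety endpoint is defined inconsistently within the SAP: MAE includes all other adverse device effects in 1.4.1 and excludes them in the reporting scheme of 3.3, and the serious-only headline does not fit the list beneath it. The harm is a mislabelled MAE rate in the literature comparison. The composite is unchanged and no data are lost.

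The size of the label difference is c/n, which may be zero and cannot be estimated from the SAP. The conclusion rests on the wording alone and on no assumed event rate. Whether a particular comparison would mislead depends on the event definitions in the literature used, which the SAP does not give.

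The counting rule and the treatment of Attempt subjects belong with this point because they fix the numerator and denominator of the same rates. The first is an unwritten rule with a probable intent. The second is a direct contradiction between sections 2 and 3.3.

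**What to change.** - Use three labels throughout 1.4.1, 3.3 and the 30- and 50-subject sub-analyses: *named MAEs* (the first ten bullets of 1.4.1), *other SADEs/ADEs* (those that are not already named MAEs) and *combined* (either, which is the primary composite). The second label also settles whether a device-caused named event counts twice across the separate rates, which the reporting sentence of 3.3 leaves unsaid.
- Reconcile the serious-only headline of 1.4.1 with its list, in line with the protocol.
- Define each rate in 3.3 as subjects with at least one qualifying event, divided by Attempt plus Treated subjects, each subject counted once per rate. Put the exact binomial 95% interval on that proportion only, and show event counts without a binomial interval.
- Align the Attempt definition in section 2 with the denominator that 3.3 states.
- Editorial: correct the pointers to 2.4.1 (in 3.3) and 2.4.4 (in 3.6) to 1.4.1 and 1.4.4.

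The cost is SAP wording and a subject-level flag in the programs. No new data are needed, and the primary composite does not change.
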